6.5. Analysis Sets

Three analysis sets will be used.

Screening Set: all subjects who give written informed consent and enter screening. The Screening Set consists of two mutually exclusive subgroups:

- subjects who were not randomized at completion of screening, generally due to failure of one or more of the study entry criteria (ie, the inclusion/exclusion criteria) and
- subjects who were randomized at completion of screening

All Randomized Set: all randomized subjects. Subjects will be evaluated by their randomized treatment arm ('intent-to-treat' analysis) unless otherwise specified. The All Randomized Set will be the primary set for efficacy analyses.

Safety Set: all randomized subjects who take at least one dose of study drug. Subjects will be evaluated by their randomized treatment arm ('intent-to-treat' analysis) unless otherwise specified. The Safety Set will be the primary set for safety summaries. Safety summaries may also be provided based on the treatment actually received.

Achieve will approve the list of subjects to be excluded from the Safety Set after database lock. Achieve must approve this list before any analysis is to be performed.

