9.3. Receipt and Storage

The Study Drug will be supplied in 1-week treatment blister packs with 6 individual weekly blister packs in a carton (6 weeks of treatment). Each subject will be assigned 2 cartons for completing the 84 days (12 weeks) of study treatment. The first carton will be assigned on Day 0 and the second carton will be assigned on Day 35 (Week 5) so that treatment can follow assigned treatment arm ([Figure 2](#)). A clinical supplies management vendor will label, package, and distribute study drug to the sites.

Drug supply will be managed via an IRT program to maintain predetermined stock levels at the sites and/or handle resupply using site initiated requests. Upon receipt, details of study drug supplied shall be documented using the IRT and/or internal site login procedures.

The study drug shall be stored in a secure, temperature controlled location and only dispensed by suitably trained staff.

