16.2. Analysis Sets

Screening Analysis Set: The Screening Analysis Set is defined as all subjects who give written informed consent and have entered screening but are not randomized. Analyses in this population will be restricted to presentation of baseline data and reasons for non-participation only.

Safety Analysis Set: The Safety Analysis Set (SAS) is defined as all randomized subjects who take at least one dose of study drug. All safety analyses will be performed on the Safety Analysis Set.

Efficacy Analysis Set: The All Randomized Analysis Set (ARS) is based on the ‘intention-to-treat’ principle and will include data from all randomized subjects.

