3.4. Safety Objectives

1. To evaluate the safety profile of 3 mg TID cytisinicline compared to placebo (Arm B vs Arm A; Arm C vs Arm A).
2. To compare the safety profiles of Arm B subjects versus Arm C subjects with respect to adverse events occurring after Week 6 on the study.

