7.1. Protocol Deviations

Protocol deviations will be reported as outlined in the ACH-CYT-04 Monitoring Plan and documented in the CRF. Each deviation will be classified as either “major” or “minor”. Major deviations are defined in the monitoring plan as those requiring direct/immediate escalation to the Sponsor/Medical Monitor in order to determine if the deviation could affect study results or the subject’s study participation. These include deviations in the following categories:

- Inadequate informed consent procedures,
- Violations of inclusion/exclusion criteria,
- Errors in randomization/stratification,
- Errors in study drug administration such that the planned and actual treatment are discrepant (eg, subject assigned to Arm A [placebo] receiving treatment prescribed for Arm B [cytisinicline 6 weeks]),
- Missing results from screening assessments used for determining subject eligibility.

The number and percentage of subjects with at least one deviation (major or minor) and with at least one major deviation will be summarized by treatment arm. For major deviations, the number and percentage of subjects with each type of deviation (eg, informed consent, inclusion/exclusion violation, etc) will be summarized by treatment arm.

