11. SAFETY ANALYSIS

Safety objectives are described in Section 3.4. All safety analyses described below will be presented for each treatment arm using the Safety Set (see Section 6.5).

Safety analyses that are presented “by visit” will include a derived visit named EOT (see Section 4.2.1.4). This includes summaries of hematology and serum chemistry test results, vital signs, weight, and 12-lead ECG results.

No statistical comparisons between treatment arms are planned for safety endpoints; thus, no statistical test results will be reported.

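### Safety tables use the randomized arm and leave treatment-received tables optional, so any dosing error would be counted under a treatment the subject did not take

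*SAP*

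**What the plan says.** SAP 6.5 defines the Safety Set as randomized subjects with at least one dose and states the assignment rule: "Subjects will be evaluated by their randomized treatment arm ('intent-to-treat' analysis) unless otherwise specified". It continues: "The Safety Set will be the primary set for safety summaries". Tables by treatment received are permitted but not required: "Safety summaries may also be provided based on the treatment actually received". No trigger is given for producing them, and no rule says how a subject with mixed exposure would be classified.

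SAP 11 specifies nothing different. It presents all safety analyses by treatment arm on the Safety Set and points back to 6.5. Protocol 16.2 settles membership only: "The Safety Analysis Set (SAS) is defined as all randomized subjects who take at least one dose of study drug". Neither 16.2 nor 16.7 says whether a subject counts under the randomized or the received arm.

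SAP 7.1 lists this among the major deviations: "Errors in study drug administration such that the planned and actual treatment are discrepant". Its example is a placebo-arm subject who receives Arm B treatment. Such deviations are escalated and tabulated by type and arm, but nothing moves the subjects in the safety tables.

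**The concern.** For safety, attenuation towards no difference is the unfavourable direction in which to err. A reaction to cytisinicline in a placebo-arm subject given active drug by mistake would appear as a placebo event.

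The design adds a particular exposure. Protocol 9.3 says: "Each subject will be assigned 2 cartons for completing the 84 days (12 weeks) of study treatment". Arms B and C are identical in the first carton and differ only in the second, and the second safety objective in SAP 3.4 rests on that difference: "To compare the safety profiles of Arm B subjects versus Arm C subjects with respect to adverse events occurring after Week 6 on the study". SAP 11.1 also plans a summary of events between the Week 6 and Week 7 visits, to look for withdrawal effects when Arm B switches to placebo. An Arm B subject wrongly given an active second carton never switched, yet would be counted there as having done so.

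The optional wording matters too. Protocol 16 requires the SAP to be final before unblinding. Even so, the decision to produce treatment-received tables, and the way mixed exposure is classified in them, could still be made with results in view.

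**Working it through.** The plan states no figure on this point, so there is none to reproduce. The check is a reading of the rule followed by an illustration of size.

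**Step 1: does anything override the default?** SAP 6.5 allows exceptions where specified. SAP 11 and Protocol 16.2 and 16.7 contain none. The randomized-arm rule therefore governs all the safety summaries in SAP 11.

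**Step 2: one event.** With 250 subjects per arm (SAP 2.2), one event counted in the wrong arm changes that arm's incidence by about 1/250 = 0.4 percentage points.

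**Step 3: average dilution.** Let p0 and p1 be the true event risks on placebo and active, k the number misdosed per affected arm, and f = k/250. Assume that misdosing covers the whole course and is unrelated to a subject's risk.

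- One-way error (k placebo-arm subjects take active): observed difference = p1 − [p0(1 − f) + p1·f] = (p1 − p0)(1 − f).
- Swap (k in each arm): observed difference = (p1 − p0)(1 − 2f).

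The same formulas apply to Arm C versus Arm B after Week 6 when the second carton is wrong.

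The risks are assumptions for this trial, taken from the range in Protocol Table 3 (ORCA-1). Abnormal dreams occurred in 2.0% on pooled placebo, 6.0% on 3 mg TID and 14.0% on 3 mg titration. The documents do not give k, so 1 to 25 is an assumed range.

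| p0 → p1 | k | f | True difference (points) | One-way | Swap |
|---|---|---|---|---|---|
| 2% → 6% | 1 | 0.004 | 4.00 | 3.98 | 3.97 |
| 2% → 6% | 5 | 0.02 | 4.00 | 3.92 | 3.84 |
| 2% → 6% | 25 | 0.10 | 4.00 | 3.60 | 3.20 |
| 2% → 14% | 1 | 0.004 | 12.00 | 11.95 | 11.90 |
| 2% → 14% | 5 | 0.02 | 12.00 | 11.76 | 11.52 |
| 2% → 14% | 25 | 0.10 | 12.00 | 10.80 | 9.60 |

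Where p1 = p0 there is nothing to dilute. For common events and a handful of errors the effect is negligible.

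**Step 4: rare events.** If two active-arm subjects and one placebo subject have a serious event by treatment received, and one of the two active events belongs to a subject randomized to placebo, the table shows 1 versus 2. This needs the same subject to be misdosed and to have the event. If 1 to 10 subjects are misdosed and the serious-event risk is 1% to 3% (both assumed), the expected number of such events is 1 × 0.01 = 0.01 to 10 × 0.03 = 0.3.

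**The case against.** The strongest reply is that the problem is conditional and already partly covered. Naming a deviation category is not evidence that errors will happen. Cartons are coded by an independent vendor (Protocol 7.3.3) and supplied through the interactive response system, including the second carton at Week 5 (Protocol 9.3 and 12.2.3). Any discrepancy is a major deviation, escalated and tabulated by arm, so a reader of the report would know that it occurred. The SAP permits treatment-received tables. Serious events are listed individually (SAP 11.1.1) and the data safety monitoring committee reviews them all (Protocol 15.1). SAP 11 plans no between-arm tests for safety, and ORCA-1 had no serious adverse events among 254 subjects.

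All of this stands, and it limits the size of the point. It also disposes of two stronger inferences that a reader might draw: that events will in fact be charged to the wrong arm, and that a serious-event comparison is likely to be reversed. The documents support neither. The first requires errors for which they give no count; the second requires a coincidence with an expected frequency well below one under the ranges above.

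Nor does the SAP contradict the protocol, which is silent on assignment. What survives is narrower: the foreseen case is identified and counted, but the main safety tables do not correct for it, and the tables that would are discretionary.

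**Conclusion.** The point holds as a low-priority correction. The primary safety tables follow the randomized arm, and tables by treatment received are neither primary nor required. If dosing errors occur, between-arm differences are diluted on average by a factor of (1 − f) or (1 − 2f), and each misattributed event shifts an arm by about 0.4 points. The comparison that depends on the second carton, Arm B versus Arm C after Week 6, is exposed along with the placebo comparisons.

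The size rests on an unknown number of errors, probably small, and on the simplifying assumption of whole-course misdosing. No test and no type I error rate is affected. The text does not show that any safety conclusion would change.

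**What to change.** In SAP 6.5, make treatment actually received the primary assignment for the Safety Set, classified by the carton sequence taken: placebo/placebo = Arm A, active/placebo = Arm B, active/active = Arm C. Keep the randomized-arm summaries as supportive, and list every subject whose received and randomized treatment differ.

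Two cases need a stated rule:

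- Placebo followed by active matches no arm. One option is to report these subjects separately, with events attributed by the period in which active drug was taken.
- A subject who stops before the second carton has an incomplete sequence, and active alone fits both B and C. Keeping the randomized arm when the first carton was correct would settle most of these. A subject given the wrong first carton who then stops needs an explicit placement.

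A shorter rule that moves anyone given active drug in error to an active arm would not do. It has no home for placebo/active, and it would leave in Arm C a subject who mistakenly received a placebo second carton and so followed Arm B's sequence.

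The cost is a short classification paragraph and, only if errors occur, a second set of safety tables. SAP 9.2 already derives the total cytisinicline dose taken, so the exposure information is needed in any case.

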7. SUBJECT DISPOSITION

The number of subjects who were screened, screen failures, randomized and treated will be summarized overall for the Screening Set. The reason for failing screening will also be summarized.

The number of subjects who were screened, randomized, treated, completed or withdrew from study, as well as the number of subjects in each analysis set will be summarized for each treatment arm. In addition, the number of subjects randomized and treated will be summarized by investigational site for each treatment arm.

For subjects who did not complete the study, the reasons for withdrawal (eg, adverse event, withdrawal by subject, lost to follow-up) will be summarized for each treatment arm. The list of subjects who withdrew from the study will be reported, along with the reason for withdrawal.

For the Safety Set the number of subject randomized, treated, completed, or withdrew from the study as well as the number of subject in each analysis set will be summarized for each treatment arm. For subjects who did not complete the study, the reasons for withdrawal (eg, adverse event, withdrawal by subject, lost to follow-up) will be summarized for each treatment arm. The list of subjects who withdrew from the study will be reported, along with the reason for withdrawal. In addition, the number of subjects randomized and treated will be summarized by investigational site for each treatment arm.

A listing will be provided of subjects who were excluded from either the All Randomized Set or the Safety Set. The listing will include the reason for exclusion.

Attendance at each study visit will be reported with the number and percentage of subjects who attended each visit (ie, Screening #1, Screening #2, Day 0 (randomization), Day 1 (treatment start), etc). Similarly, the last study visit attended will be reported with the number and percentage of subjects having their last study visit at Week 24, Week 20, etc.

The number and percentage of subjects who completed the treatment period, and enter the follow-up period (ie, attended the Week 16 or Week 20 or Week 24 visit) will be reported.

A Kaplan-Meier figure will be produced by treatment arm of time to last recorded data related to the abstinence endpoints (ie, time from date of randomization to date of last smoking cessation data recorded at or prior to the Week 24 visit). If a subject is randomized and not treated (no visits after Day 0) then time from randomization to last recorded data would be 0 days. The date of the last smoking assessment data will be the date of the last self-report of cigarette smoking since the last clinic visit (yes, no), self-report of cigarette smoking over the past 7 days (yes, no) or expired CO levels.

7.1. Protocol Deviations

Protocol deviations will be reported as outlined in the ACH-CYT-04 Monitoring Plan and documented in the CRF. Each deviation will be classified as either “major” or “minor”. Major deviations are defined in the monitoring plan as those requiring direct/immediate escalation to the Sponsor/Medical Monitor in order to determine if the deviation could affect study results or the subject’s study participation. These include deviations in the following categories:

- Inadequate informed consent procedures,
- Violations of inclusion/exclusion criteria,
- Errors in randomization/stratification,
- Errors in study drug administration such that the planned and actual treatment are discrepant (eg, subject assigned to Arm A [placebo] receiving treatment prescribed for Arm B [cytisinicline 6 weeks]),
- Missing results from screening assessments used for determining subject eligibility.

The number and percentage of subjects with at least one deviation (major or minor) and with at least one major deviation will be summarized by treatment arm. For major deviations, the number and percentage of subjects with each type of deviation (eg, informed consent, inclusion/exclusion violation, etc) will be summarized by treatment arm.

8. DEMOGRAPHIC AND OTHER BASELINE CHARACTERISTICS

Demographic and other baseline characteristics will be listed and summarized.

8.1. Demographics

Demographic data (gender, age informed consent, race, ethnicity, body weight, height, and BMI) will be summarized for each of the subgroups (Randomized, Not Randomized) in the Screening Set, and overall.

Demographic data will also be summarized by treatment arm and overall for both the All Randomized Set and the Safety Set.

8.2. Medical and Psychiatric History

A medical and psychiatric history summary will be provided for both the All Randomized Set and the Safety Set. The number and percentage of subjects with events will be summarized for each treatment arm by MedDRA SOC and preferred term. Multiple occurrences of the same event within a subject will be counted only once.

Medical and psychiatric history conditions will be coded using MedDRA version 23.1.

8.3. Prior Medications

Concomitant medications will be recorded beginning at the Screening #1 (SV1) visit. Prior medications will be defined as medications with a stop date prior to the first dose of study drug. For medications with partial dates, these will be imputed as specified in Section 6.4.1; safety related dates. Prior medications will be summarized for both the All Randomized Set and the Safety Set. The number and percentage of subjects with each prior medication will be summarized for each treatment arm by highest available Anatomical Therapeutic Chemical (ATC) class and preferred name. Multiple occurrences of the same medication within a subject will be counted only once.

Prior medications will be coded using WHO Drug Dictionary March 2021.

8.4. Smoking History

Smoking history will be summarized for both the All Randomized Set and the Safety Set.

At SV1 the following subject-reported smoking history variables will be summarized by treatment arm.

- Duration of smoking (years) – started smoking date minus the screening 1 visit date.
- Average number of cigarettes the subject reported smoking per day over the past 30 days

- Type of cigarettes typically smoked (regular vs menthol)
- Number (%) of subjects who attempted to quit in the past
- Number of previous quit attempts
- Time from last quit attempt to date of SV1 visit (months) – screening 1 visit date minus date of last quit attempt. If month of last quit attempt date is unknown use December of that year, unless the quit date year is the same year as the screening 1 visit date then December of the previous year would be used.

In addition, the number (%) of subjects reporting past use of various smoking cessation treatments will be summarized separately for the most recent quit attempt and all quit attempts. For each of these summaries, multiple occurrences of the same treatment within a subject will be counted only once.

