8.1. Inclusion Criteria

Subjects must meet ALL of the following criteria to be eligible for inclusion into the study:

1. Male or female subjects, age ≥ 18 years.
2. Current daily cigarette smokers (averaging at least 10 cigarettes per day upon completing a 7-day screening smoking diary) and who intend to quit smoking.
3. Expired air carbon monoxide (CO) ≥ 10 ppm.
4. Failed at least one previous attempt to stop smoking with or without therapeutic support.
5. Willing to initiate study treatment on the day after randomization and set a quit date within 5-7 days of starting treatment.
6. Willing to actively participate in the study's smoking cessation behavioral support provided throughout the study.
7. Able to fully understand all study requirements, willing to participate, and comply with dosing schedule.
8. Sign the Informed Consent Form.

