6.4.1. Missing Dates

Partial or missing dates will be imputed only if a date is required to derive a study endpoint (eg, time to failure, duration of AE) or a variable used in study analyses. Otherwise no date imputation will be done. Date imputation will follow the rules below.

Efficacy Related Dates

Partial or missing dates required to compute efficacy endpoints will be imputed as follows:

- Missing day only: For partial dates with only the day of the month missing, the day will be imputed as the 15th day of the month, provided that a preceding date of interest does not occur in the same month. If the preceding date does occur in the same month, then the missing day will be imputed as half the distance between the preceding date and the end of the month. For example, if the Week 2 visit occurs on the 15th day and Week 3 day was missing, Week 3 day could not be day 15, it would be day 22.
- Missing month and day: For partial dates with the month and day missing, the month and day will be imputed as July 1st, provided that a preceding date of interest does not occur in the same year. If the preceding date occurs in the same year, then the month and day will be imputed as half the distance from the preceding date to the end of the known year.
- Missing month, day, and year: Missing dates will be imputed as the date of first dose.
- In situations where the above rules result in an illogical time (eg, negative study day, negative time to failure, etc) the date will be imputed as the date half the distance between the preceding date of interest and the partial date.

Safety Related Dates

For medications occurring prior to first dose of study drug. Missing or partial date will not be imputed. For safety data besides medications where the date of onset is during or after administration of the first dose of study drug, missing or partial start dates will be imputed as the earliest possible date that is on or after the date of the first dose of study drug. For events occurring prior to first dose of study drug, missing or partial dates will not be imputed.

- Missing day only: If the start date and date of first dose share the same month and year, the missing start day will be imputed as the day of first dose. If the start date month is after the month of first dose, day will be imputed as the 1st (ie, 01-Jan-2019).

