10.2.9. Relationship Between Treatment Effect and Demographic and Baseline Characteristics

The analyses described below will only be performed for the primary efficacy endpoint (biochemically verified abstinence). The objective of these analyses is to assess the homogeneity of treatment effect within strata (subgroups) defined by potential effect-modifying variables. If both primary comparisons (Arm B vs Arm A, Arm C vs Arm A) performed for the primary efficacy endpoint do not meet statistical criterion (ie, are not statistically significant) then the statistical analyses described below will not be performed. If only one of the comparisons meets

statistical criterion then the analyses described below will be performed using data from only two of the treatment arms.

Strata for continuous effect modifiers will be defined by either logical considerations (eg, age >65 years) or statistical criteria (eg, quantile (median, tertile or quartile) split). The variables (factors) that will be evaluated as effect modifiers include, but are not limited to:

- demographic characteristics (eg, sex, age, race, BMI),
- smoking history variables (eg, duration of smoking, average number of cigarettes the subject reported smoking per day over the past 30 days, number of previous quit attempts, type of cigarettes typically smoked: regular vs menthol, prior smoking cessation treatment with varenicline, bupropion, nicotine patch),
- baseline smoking variables (eg, average number of cigarettes smoked per day over 7 consecutive days as reported in the subject diary, baseline CO (ppm), baseline cotinine (ng/mL)),

For each stratum, the number (%) of subjects within each stratum with biochemically verified abstinence will be reported for each treatment arm. Odds ratios (Arm B vs Arm A, Arm C vs Arm A) and their 95% CIs will also be reported. Forest plots will be used to display the stratum-specific 95% CIs.

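### SAP 8.4 writes duration of smoking with the subtraction reversed, and its missing-month rule moves a same-year quit attempt into the previous year

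*SAP*

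**What the plan says.** SAP 8.4 (Smoking History) lists baseline variables taken at the first screening visit (SV1).

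- **Duration of smoking, in years:** "started smoking date minus the screening 1 visit date".
- **Time from last quit attempt, in months:** "screening 1 visit date minus date of last quit attempt".
- **Unknown quit month, general rule:** "If month of last quit attempt date is unknown use December of that year".
- **Unknown quit month, exception for attempts in the year of SV1:** "unless the quit date year is the same year as the screening 1 visit date then December of the previous year would be used". Neither rule gives a day within December.

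SAP 10.2.9 names "smoking history variables (eg, duration of smoking" among the candidate effect modifiers for the primary endpoint. It allows strata for continuous modifiers to come from logical cutpoints or from quantiles, and it does not say which applies to duration. Protocol 12.2.1 asks at screening for the year in which the subject started smoking and mentions no month or day.

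**The concern.** Protocol 8.1 admits "Current daily cigarette smokers (averaging at least 10 cigarettes per day upon completing a 7-day screening smoking diary", so the start of smoking comes before SV1. Subtracting the later date from the earlier one then gives a negative number of years. The quit-attempt line in the same list has the dates in the opposite, sensible order, so the reversal looks like a slip and not a convention.

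The quit-month rule overrides a fact that was collected. A subject known to have tried to quit in the screening year is treated as having tried in the previous year. An attempt recorded in the previous year with unknown month gets that same December, so the two can no longer be told apart.

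At stake are two lines of the baseline table and one input to an exploratory subgroup analysis. SAP section 1 says the final analyses will follow the SAP and that deviations will be documented in the study report. A silent correction by the programmer would therefore be an undocumented deviation. The quit-attempt error is also hard to spot, because its values are positive and plausible.

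**Working it through.** The SAP states no numerical result for either variable, so there is no figure to reproduce. The check is date arithmetic on the written rules.

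**Duration.**

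- Input, for illustration: mean 32.1 years as a smoker, SD 13.7, printed as a positive number in Protocol 4.3 (ORCA-1).
- As written: start - SV1 = -32.1 years. Reversed: SV1 - start = +32.1 years. Likewise -1, -10 and -50 in place of 1, 10 and 50.
- In the baseline summary the mean and median change sign, the minimum and maximum change sign and trade places, and the SD is unchanged.

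**Effect on strata.** This used 750 simulated durations, assumed normal with mean 32.1 and SD 13.7 and floored at 1 year.

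- Quartile split: negation reverses the ranks, so the lowest quartile as written is the true highest. Group membership matched for 100% of subjects after reversing the order. The simulated values were continuous; with year-only data, ties at a cut would need a convention in either direction.
- Fixed cutpoint, assumed at 20 years or more: 602 of 750 lie above it with the correct sign and 0 of 750 with the written formula.

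**Unknown quit month, same year as SV1.** The attempt lies between 1 January and SV1, so the possible interval runs from 0 to (SV1 - 1 January). The rule gives SV1 minus a day in the previous December; the range below covers 31 December to 1 December. SV1 dates are assumed, and a month is 30.4375 days.

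| SV1 date | Possible interval (months) | Imputed interval (months) |
|---|---|---|
| 31 January | 0 to 1.0 | 1.0 to 2.0 |
| 15 March | 0 to 2.4 | 2.4 to 3.4 |
| 15 June | 0 to 5.4 | 5.5 to 6.4 |
| 15 September | 0 to 8.4 | 8.5 to 9.5 |
| 15 December | 0 to 11.4 | 11.5 to 12.5 |

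The imputed date always precedes 1 January of the recorded year, so the imputed interval is never shorter than the longest possible true one. If the attempt is uniform between 1 January and SV1, the average excess for SV1 on 15 June is 5.5 - 2.7 = 2.8 to 6.4 - 2.7 = 3.7 months. For 15 December it is 11.5 - 5.7 = 5.8 to 12.5 - 5.7 = 6.8 months. For one subject with an attempt shortly before a December screening, the error can reach about 12 months.

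**Unknown quit month, earlier year.** December is the latest possible month. With months uniform from 1 to 12 the mean is 6.5, so the interval is too short by 12 - 6.5 = 5.5 months on average. For scale, Protocol section 5 puts the last attempt in ORCA-1 at about 3.7 years before entry, or 3.7 x 12 = 44.4 months, and 5.5 / 44.4 is about 12% for an affected subject.

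**The case against.** The strongest reply is that the sign slip is editorial. The line is labelled as a duration in years, the neighbouring line shows the intended order, and a column of negative durations would be seen in the first output. That is fair as to likelihood, but it does not make the written rule right.

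Three further points on the other side stand.

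- A reader might infer that the subgroup results for duration would be corrupted. The documents do not support that. SAP 10.2.9 does not assign quantiles to duration, a quantile split leaves stratum estimates and the interaction P value unchanged, and no fixed cutpoint for duration is stated. The analyses are exploratory and are not run if both primary comparisons fail.
- A reader might infer that the December rule conflicts with SAP 6.4.1, where "the month and day will be imputed as July 1st". That rule stands under efficacy-related dates and is conditional on no preceding date of interest in the same year. Baseline quit history is not an efficacy endpoint, so 6.4.1 does not govern 8.4.
- The previous-December fallback has an evident purpose. December of the SV1 year would usually fall after SV1: 15 December against SV1 on 15 June gives -6.0 months. The rule avoids a negative interval, but at the price of contradicting the recorded year. It applies alike in all arms, so it creates no systematic difference between them.

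**Conclusion.** Both rules are wrong as written, at low severity. Duration has the wrong sign for any start date before SV1. To say that every subject would be negative goes slightly too far: only the start year is collected and 8.4 gives no month or day, so a subject who started in the SV1 year could get zero or either sign depending on the convention used.

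The consequence is a baseline line with the wrong sign and, in the exploratory modifier analysis, swapped labels under a quantile split or an unusable split under a fixed cutpoint.

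The quit-month rule lengthens same-year intervals and shortens earlier-year ones. The average sizes above assume a uniform month. The documents do not say how many subjects have an unknown month or a same-year attempt, so the effect on the summary cannot be sized. Time since last quit attempt is not among the modifiers listed in SAP 10.2.9. That list is not exhaustive, but as written this part touches only a descriptive baseline variable.

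No primary or secondary test, significance level or sample size depends on either variable.

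**What to change.** In SAP 8.4:

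1. Define duration of smoking as SV1 date minus start date, converted to years, and state a convention for year-only start dates, including a start in the SV1 year. Without that convention the corrected formula cannot be programmed.
2. Impute an unknown quit month within the recorded year and no later than SV1. For example, use the midpoint of 1 January and SV1 when the year is the SV1 year, and mid-year for earlier years. State the day as well.

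The mid-year choice for earlier years is a suggestion that removes the average shortening; 6.4.1 does not require it. The cost is about two lines of SAP text and the matching dataset specification. No new data are needed.
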